1.1. Synopsis

Title:	Toward Thriving Study
Grant Number:	N/A
Study Description:	A longitudinal clinical trial in a cohort of chronic pain to assess feasibility of a new behavioral intervention based on the principles of positive psychology. The study will recruit 20 participants, who will complete 4 timepoints (T1-T4). Participants will be consented at T1. T2 will be a kickoff meeting for all participants. After T2, participants will complete study intervention phase 1 (cultural probe kit) for three weeks. Next participants will participate in a facilitated workshop at T3, complete phase 2 of the intervention, followed by an exit interview at T4. Participants will complete a study survey at T1 and T4.
Objectives*:	The purpose of this pilot study is to introduce and test a positive psychology intervention meant to empower chronic pain patients and help support their resiliency and thriving.
Endpoints*:	
 Primary: Feasibility and acceptability of the behavioral intervention (cultural probe kit related activities). Percent (%) of participants engaging in the intervention between T1 and T4 Secondary: Change in PGIC between T1 and T4 Change in PROMIS Pain Interference between T1 and T4 Exploratory: Change in PROMIS 29 depression, anxiety sleep, fatigue between T1 and T4
Study Population:	Participants over the age of 18 with chronic pain
Description of Sites/Facilities Enrolling Participants:	This study will recruit patients at the Michigan Medicine. There will be no sites outside of the US.
Description of Study Intervention/Experimental Manipulation:	Participants will complete a cultural probe kit over 3-weeks. This kit is a design research tool, to prompt participants to document, map, journal, and reflect on various aspects of their daily lives
Study Duration*:	12 months
Participant Duration:	4 months

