3.4.3. Incentives

Participants will be paid up to \$250. They will receive \$150 for completing the workshop (T3) and associated intervention phase 1 kit and \$100 for completing the exit interview and associated phase 2 activities

4. Study Intervention

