5.1. Acceptability Study

We will conduct semi-structured interviews to understand participant perception of the intervention at T4. We will assess the proportion of participants who report that the intervention was relatively easy to understand after orientation, low burden (easy to do), and potentially effective.

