5.1.1. Hypothesis

≥80% of participants will report that the intervention was relatively easy to understand after orientation, low burden, and potentially effective.

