5.2.3. Hypothesis test and power analysis

Frequencies will be calculated related to feasibility data (e.g., number of participants approached, consented, and take part in the workshop). Descriptive statistics of patient-reported outcomes will be calculated before and after the intervention. Paired t-tests are used on patients' changes from T1 to T4. Wilcoxon test will be applied if departure from the assumption of normality. Hypotheses tests are two-sided performed at the 5% significance level. 95% confidence interval will be conducted. Power analysis for efficacy is based on t-tests.

6. Study Intervention Discontinuation and Participant Discontinuation/Withdrawal

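### The only T4 payment covers the exit interview and Phase 2 activities together, so T4 results, including acceptability, may over-represent people who finished Phase 2

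*Combined protocol and SAP*

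**What the plan says.** **Payment.** Section 3.4.3 opens with "Participants will be paid up to" $250 and splits this into two parts. The first $150 is "for completing the workshop (T3) and associated intervention phase 1 kit"; the remaining $100 is "for completing the exit interview and associated phase 2 activities". Each part joins a visit to a set of home activities. No partial amount is given, and the T4 survey is not mentioned.

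**What depends on T4.**
- Acceptability: Section 5.1 states "We will conduct semi-structured interviews to understand participant perception of the intervention at T4", and Section 5.1.2 makes the participant's assessment a primary outcome. The hypothesis in 5.1.1 is that at least 80% of "participants will report that the intervention was relatively easy to understand after orientation, low burden, and potentially effective". Whether the denominator is those enrolled, those who started or those interviewed is not stated.
- Patient-reported outcomes: the synopsis says "Participants will complete a study survey at T1 and T4", and the schedule of activities (Section 1.3) lists PGIC at T4 only. Section 5.2.3 says "Paired t-tests are used on patients' changes from T1 to T4". No method for missing T4 data is given.

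**People who stop.** Section 6.1 counts discontinuing the intervention as withdrawing from the study. Section 6.2 lets the investigator withdraw a participant for significant non-compliance. No T4 collection is described for either group.

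**The concern.** Low burden is one component of the acceptability outcome. A participant who found Phase 2 burdensome and left part of it undone is a likely source of an unfavourable rating. That same participant has no stated payment for coming to T4. The incentive to supply the data is thus linked to the quantity being measured.

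If such people attend less often than finishers, the observed acceptability proportion exceeds the proportion among all participants, and the T4 symptom data come from a selected group. With 20 participants, a handful of absent interviews can decide whether the 80% mark is reached, and nothing in the analysis plan would correct for it.

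**Working it through.** The plan gives no completion, attendance or dropout rate for this point, so there is no planned figure to reproduce. The payment amounts do add up: $150 + $100 = $250.

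**Step 1. What absent interviews can do, with no assumption about who is absent.** Input: N = 20 (synopsis). With m people not interviewed, n = 20 − m, and the smallest count that reaches 80% is r = 0.8n rounded up. Over all 20, the proportion lies between r/20 (all absentees unfavourable) and (r + m)/20 (all favourable).

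| m absent | Smallest passing result | Range over all 20 |
|---|---|---|
| 0 | 16/20 = 80% | 80% |
| 2 | 15/18 = 83% | 75% to 85% |
| 4 | 13/16 = 81% | 65% to 85% |
| 6 | 12/14 = 86% | 60% to 90% |

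Even with nobody absent, 16/20 has an exact (Clopper-Pearson) 95% interval of 56% to 94%.

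**Step 2. Expected shift if non-finishers attend less often.** All inputs here are assumptions: 85% of finishers and 40% of non-finishers are favourable, and 95% of finishers attend. Let q be the share of non-finishers and s their attendance.

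- All-participant rate = (1 − q)(0.85) + q(0.40)
- Observed rate = [(1 − q)(0.95)(0.85) + q·s·(0.40)] / [(1 − q)(0.95) + q·s]

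Example with q = 0.20 and s = 0.50: the all-participant rate is 0.68 + 0.08 = 76.0%. The observed rate is (0.646 + 0.040)/(0.76 + 0.10) = 0.686/0.86 = 79.8%, a shift of 3.8 points.

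| q | All-participant rate | Shift, s = 95% | s = 50% | s = 25% | s = 0 |
|---|---|---|---|---|---|
| 10% | 80.5% | 0 | 2.0 | 3.2 | 4.5 |
| 20% | 76.0% | 0 | 3.8 | 6.2 | 9.0 |
| 30% | 71.5% | 0 | 5.2 | 8.9 | 13.5 |
| 40% | 67.0% | 0 | 6.3 | 11.3 | 18.0 |

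Shifts are in percentage points. They are zero when both groups attend equally and reach 18 points at the far corner.

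**Step 3. Chance of observing at least 80%.** A second assumed case: 14 finishers, all interviewed, 90% favourable; 6 non-finishers, 40% favourable. The all-participant rate is (14 × 0.9 + 6 × 0.4)/20 = 15/20 = 75%. Summing the binomial probabilities exactly over attendance and responses gives:

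| Non-finisher attendance | Mean observed rate | P(observed ≥ 80%) |
|---|---|---|
| 100% | 75% | 0.388 |
| 80% | 77% | 0.385 |
| 70% | 79% | 0.44 |
| 50% | 81% | 0.60 |
| 0% | 90% | 0.84 |

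The chance of passing barely moves while about 80% of non-finishers attend. It rises sharply only when half or more stay away.

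**The case against.** A reader might infer that the payment rule makes T4 data selectively missing and inflates acceptability as a matter of fact. The documents do not support that. They give no Phase 2 completion or T4 attendance rate, and nothing shows how far $100 changes attendance, particularly as Section 4.3 allows T4 to be virtual. The calculations show what differential attendance does from any cause; they do not attribute it to payment. This objection stands, and only *may* is justified.

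A reader might also infer that payment is the main reason non-finishers would be missing. Sections 6.1 and 6.2 argue against this: someone who stops the intervention counts as withdrawn whatever the payment rule, so a payment edit alone would not bring in that person's interview. This stands too. But neither section says that doing part of Phase 2 is discontinuation, and withdrawal for non-compliance is discretionary. Part-completers who stay enrolled remain exposed to the payment rule.

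Third, completing is undefined, the total is expressed as a maximum, and payment details may appear in the consent form, which was not available here. Part-completers might be paid in practice. The text therefore does not establish that they are refused payment, but neither does it tell them that they would be paid.

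Fourth, Section 5.2 counts exit interviews, 5.2.2 tracks loss to follow-up and 6.3 requires repeated contact after missed visits. These make absence visible and may reduce it; they do not correct the estimate. Finally, tying payment to activities is a legitimate retention choice, and loosening the tie has a cost.

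**Conclusion.** The point holds as a risk that is cheap to reduce. The stated rule links the only T4 payment to Phase 2 work, while a primary outcome and all the change data depend on T4. Results may over-represent finishers, and the 80% acceptability result may be too high.

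The size is unknown. The range of 0 to about 18 percentage points assumes that non-finishers make up 10% to 40% of participants, rate the intervention much less favourably (40% against 85%) and attend no more often than finishers. If attendance is equal, or the two groups rate it alike, there is no bias. The bounds in Step 1 do not rest on those assumptions: with 4 of 20 not interviewed, a just-passing 81% is compatible with 65% to 85% overall.

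The payment rule acts mainly on people who remain enrolled and do part of Phase 2. The withdrawal provisions are a separate route to missing T4 data and need to be dealt with alongside it.

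**What to change.** 1. In Section 3.4.3, pay the $100 for completing the T4 exit interview and T4 survey, whatever share of Phase 2 was done. Match the consent wording, and record Phase 2 completion as a separate item.
2. Reconcile Sections 6.1 and 6.2 with T4 data collection, so that T4 data are sought, with the participant's agreement, from people who stop the activities.
3. In Section 5.1, define the acceptability denominator as everyone who started the intervention. Report the number interviewed, and add a sensitivity analysis that counts missing interviews as unfavourable.

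**Cost.** A protocol amendment and consent wording. Nobody exceeds the existing $250 maximum, so the total stays within 20 × $250 = $5,000. The added outlay is at most $100 for each non-finisher who attends T4. The drawback is a somewhat weaker incentive to finish Phase 2, although completion that is not paid for says more about feasibility.

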4.1. Overall

Participants will complete two phases of the study intervention before and after the T3 visit. The interventions are made up of self-guided at home activities.

4.2. Phase 1 and Workshop (T3)

Participants will be using a cultural probe kit, a design research tool, to prompt participants to document, map, journal, and reflect on various aspects of their daily lives. During an interactive, in-person workshop (T3), participants will review and synthesize the contents of their probe kit and set goals for themselves. The workshop, which takes place after participants have completed three weeks of at-home activities, will be facilitated in small groups by a designer and psychologist team.

4.3. Phase 2 and Exit Interview (T4)

Participants will end the study with 3-weeks of at-home activities and an exit interview about their experience. T4 may be completed in-person or virtually and maybe recorded.

5. Statistical Design and Analysis

5.1. Acceptability Study

We will conduct semi-structured interviews to understand participant perception of the intervention at T4. We will assess the proportion of participants who report that the intervention was relatively easy to understand after orientation, low burden (easy to do), and potentially effective.

5.1.1. Hypothesis

≥80% of participants will report that the intervention was relatively easy to understand after orientation, low burden, and potentially effective.

5.1.2. Outcome

The primary outcome is the patient assessment of the cultural probe tool and the overall experience including orientation and facilitated workshop. A series of prompts in the semi-structured interview will elicit opinions about the intervention, the ease of completion, and the possibility that it could help promote positive emotions and resilience.

5.1.3. Hypothesis test and power analysis

Hypotheses tests are two-sided performed at the 5% significance level. 95% confidence interval will be conducted.

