5.2. Feasibility Study

We will collect data related to the number of participants approached and consented; the percentage consented who attend the facilitated workshop, the number of activities the participants at the workshop have completed, the number of participants who take part in the exit interview and the progress made towards goals set at the Sensemaking Workshop. We will also explore the intervention's potential to improve patient-reported outcomes including patient global impression of change (PGIC). Patient-reported outcomes will be measured before and after the intervention.

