5.2.1. Hypothesis

≥80% of participants attending the facilitated workshop will have completed at least 2 of the 3 reflective tools.

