5.2.2. Outcome

The primary outcome is the proportion of participants who attending the Sensemaking Workshop have completed at least 2 of the 3 reflective tools. The secondary outcomes are patient's belief about the efficacy of intervention (PGIC) and other symptoms including pain interference, depression, anxiety, and sleep, etc. The rate of patients being lost-to-follow-up will also be tracked to aid in appropriate design of a future randomized clinical trial.

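### Feasibility is counted only among workshop attendees, and acceptability apparently only among T4 interviewees, so both 80% benchmarks can be met while far fewer of those enrolled succeed

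*Combined protocol and SAP*

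**What the plan says.** **Acceptability.** Section 5.1.1 states the hypothesis as "≥80% of participants will report that the intervention was relatively easy to understand after orientation, low burden, and potentially effective". The data source is in 5.1: "We will conduct semi-structured interviews to understand participant perception of the intervention at T4". The denominator is described only as participants. Section 5.1.3, whose heading promises a hypothesis test and a power analysis, says "Hypotheses tests are two-sided performed at the 5% significance level" and adds that a 95% confidence interval will be produced. It names no null value, decision rule or interval method.

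**Feasibility.** Section 5.2.1 sets "≥80% of participants attending the facilitated workshop will have completed at least 2 of the 3 reflective tools", and 5.2.2 makes that same attendee-based proportion the primary outcome. Section 5.2 also plans "the percentage consented who attend the facilitated workshop" and the number taking part in the exit interview. Section 5.2.2 adds "The rate of patients being lost-to-follow-up will also be tracked". Section 5.2.3 repeats the two sentences of 5.1.3 after naming paired t-tests and the Wilcoxon test for T1–T4 changes, and ends "Power analysis for efficacy is based on t-tests".

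**Drop-outs.** Section 6.1 treats stopping the intervention as leaving the study. Section 6.2 allows replacement only of those who consent but never receive the intervention.

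**Synopsis.** The planned number is 20. The primary endpoint includes the percentage engaging in the intervention between T1 and T4, without a definition of engaging or a threshold.

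**The concern.** The people most likely to find a reflective kit burdensome are also the most likely to stop using it, miss the workshop or never reach the exit interview. If they drop out of the denominator, the benchmark is judged on those for whom the intervention worked well enough to stay. A pilot meant to inform a later randomised trial could then report that 80% was reached while a much smaller share of those enrolled completed the tools or found them acceptable.

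A second, smaller gap concerns the decision itself. A benchmark of at least 80% and a two-sided 5% test can give different answers on the same data, and 5.1.3 does not say which one governs.

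**Working it through.** **Inputs.** From the documents: 20 participants (synopsis); 80% benchmarks (5.1.1, 5.2.1); two-sided 5% level and 95% interval (5.1.3); attendee denominator (5.2.1, 5.2.2); T4-only interview (5.1); drop-out rules (6.1, 6.2). The documents give no drop-out rate, true success rate or null value, so every such value below is an assumption. There is no stated power or sample-size calculation to reproduce.

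**Step 1: how far the benchmark can drift.** If d of 20 leave, m = 20 − d are counted. The benchmark needs the smallest whole number k with k ≥ 0.8m. The share of those enrolled is k/20.

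| d | m | k | k/m | k/20 |
|---|---|---|---|---|
| 0 | 20 | 16 | 80% | 80% |
| 2 | 18 | 15 | 83% | 75% |
| 4 | 16 | 13 | 81% | 65% |
| 5 | 15 | 12 | 80% | 60% |
| 8 | 12 | 10 | 83% | 50% |

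The last column counts those who left as not having succeeded. For feasibility, 5.2 plans to count completed activities only for people at the workshop, so a non-attendee would normally have no completion record. With d = 5 the figure of 12/20 is therefore a lower bound. If all five absentees had in fact completed two tools, it would be 17/20 = 85%.

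**Step 2: intervals.** The Clopper-Pearson 95% limits for x of n are the 0.025 quantile of Beta(x, n − x + 1) and the 0.975 quantile of Beta(x + 1, n − x).
- 12/15: 51.9% to 95.7%
- 12/20: 36.1% to 80.9%
- 16/20: 56.3% to 94.3%

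**Step 3: how often the denominator matters.** Suppose each participant stays with probability r, and 90% of stayers succeed (both assumed). Over all enrolled, the number of successes is X ~ Bin(20, 0.90r), and the rule is X ≥ 16.
- No attrition (r = 1): P(X ≥ 16) = 0.957
- r = 0.90, rate 0.81: P(X ≥ 16) = 0.673
- r = 0.80, rate 0.72: P(X ≥ 16) = 0.302

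Counting stayers only, and averaging over the Bin(20, r) number who stay, the benchmark is met with probability 0.910 at both retention rates. The stayers-only rule is almost unaffected by retention; the all-enrolled rule is strongly affected.

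**Step 4: the unlinked test (illustration only).** Assume that the test in 5.1.3 is against 80%, which the plan does not say.
- 20/20: upper tail 0.8^20 = 0.0115, doubled 0.023. Score z = 0.20/√(0.16/20) = 2.236, p = 0.025. Both reject.
- 19/20: exact p = 0.156 (0.138 by doubling the tail). Score z = 0.15/√(0.16/20) = 1.677, p = 0.094. Neither rejects.

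So 16/20 meets the benchmark, but only 20/20 would succeed by the two-sided exact or score test. That happens with probability 0.9^20 = 0.122 at a true 90% and 0.95^20 = 0.358 at a true 95%. With an assumed null of 50% instead, the exact rule (upper tail at most 0.025) would be at least 15/20. The requirement follows entirely from a null value that is not stated.

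**The case against.** The plan does not ignore attrition. Attendance among those consented, exit-interview numbers and loss to follow-up are all to be reported, and the synopsis lists a percentage engaging that is not limited to attendees. A reader might infer that no proportion over all enrolled is planned; that goes too far. What stands is narrower: no all-enrolled version of the two-of-three-tools or acceptability proportion is planned. The engaging measure does not fill the gap, because it is undefined and has no threshold.

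Loss of drop-outs from acceptability is not written down. It is inferred from collection at T4 only, together with 6.1. That is correct, and the point is stated accordingly.

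A reader might also infer that the trial tests acceptability against 80% and is badly underpowered for it. The documents do not support this. No null is given, and the same wording recurs in 5.2.3 beside tests of T1–T4 changes, so it may be boilerplate with the 80% meant as a plain benchmark. A powered test is not essential in a 20-person single-arm pilot.

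Nor is the scoring as open as it may look. Sections 5.1 and 5.1.1 join the three attributes with a conjunction, so all three is the natural reading. Section 2.4 refers to exit-interview plans, and Appendix A has no content in the text available here, so further scoring detail may exist.

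Finally, counting non-interviewed participants as failures mixes retention with acceptability: 5.1.2 asks for a view of the whole experience, including the workshop, which a non-attendee cannot give. This is a sound reason not to make that convention the sole criterion.

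**Conclusion.** The concern holds as a point about denominators. Drop-outs leave the feasibility proportion by explicit definition and the acceptability proportion by inference. With five drop-outs out of 20, the benchmark can be declared met at 12/15 = 80% when 12/20 = 60% of those enrolled are shown to have succeeded. The size depends on attrition, which the documents do not predict, and on treating those without a record as not successful. With 90% success among stayers and retention of 80% to 90% (assumed), the chance of meeting the benchmark is 91% among stayers but 30% to 67% over all enrolled.

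Section 5.1.3 also leaves its test unconnected to the benchmark. That is missing detail worth a sentence. The figures for an 80% null, and any power statement, are illustrative and require no change of their own. The whole point is an inexpensive improvement in reporting and does not invalidate the design.

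**What to change.** 1. In 5.2.2 and 5.2.3, keep the attendee-based proportion. Report beside it the proportion of all participants who consented and received the kit who completed at least two of the three tools, counting no record as not completed. Give exact (Clopper-Pearson) 95% intervals for both, and base the feasibility conclusion on both.
2. In 5.1.3, state that the 80% acceptability criterion is judged on the observed proportion reporting all three attributes, with an exact 95% interval and no significance test. Report it among those interviewed and, as a sensitivity analysis, among all kit recipients with those not interviewed counted as not meeting it.
3. Use the same all-recipients denominator for both outcomes. It need not be exactly 20, because 6.2 makes replacement of those who never receive the intervention optional.
4. Limit the two-sided 5% tests to T1–T4 changes in patient-reported outcomes.

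Cost: no new visits, instruments or participants, but the wording should be settled before outcome data are seen. The all-recipients figures will be less favourable and mix retention with acceptability, which is why both denominators should be shown. The acceptability criterion becomes a point-estimate rule with a wide interval (16/20: 56–94%) and supports no significance claim.
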